5. METHODS

5.1 Study parameters/endpoints

5.1.1 Main study parameter/endpoint

Hearing preservation is the main outcome, which will be expressed in percentage. Hearing preservation is calculated by the following formula: $HP = 1 - (PTA\ post - PTA\ pre) / (PTA\ max - PTA\ pre)$. See section 5.3.

5.1.2 Secondary study parameters/endpoints

Scalar position of the electrode array (scala tympani or scala vestibuli assessed by CB-CT), ECochG (among others amplitude in μ V), and speech perception test with/without noise in CVC words correct score (in percentage).

5.2 Randomisation, blinding and treatment allocation

Patients will be randomly allocated to one of four groups. Block randomization will take place electronically by the study management system researchtool. The Julius Center will handle this randomization procedure. All groups carry the same equal weight. They will stratify the groups for age, with two subgroups, 18-50 years and > 50 years. This study is single-blind, meaning that only participants are blinded for the treatment allocation. However, research assistants will be blinded for the treatment.

5.3 Study procedures

For this study there are procedures before, during or after the cochlear implantation surgery, or pre, intra and post-operatively respectively.

Preoperatively (standard medical care): Before randomization, each participant will undertake the normal standard preoperative work-up: a CT scan, a pure tone audiogram/speech test and interviews with ENT specialist and audiologist.

Intraoperatively: all participants will undergo, according to the group they are allocated to, either a CO or RW insertion approach and receive either the PM or the LW electrode array. During and right after cochlear insertion, ECochG potentials will be recorded to study possible insertion trauma. The surgical procedures are standard medical care.

Postoperatively: all patients will receive a cone beam CT scan, to assess the scalar localization of the electrode. Upon activation of the CI, around 3-4 weeks after surgery, the first postoperative PTA/ECochG will be measured. In the following months, the PTA/ECochG is

repeated at 3, 6 and 12 months after surgery. At one year after surgery, the clinical ripple test and the standard CVC word tests with and without noise will be performed to study the eventual hearing outcome for each group. See **study design diagram** for an overview.

1. Hearing preservation

Preoperative pure tone audiometry is already a standard test to assess the eligibility for a cochlear implant for severe hearing impaired patients. With postoperative pure tone audiometry (without CI) we can calculate the hearing preservation by the following equation:

$$HP = 1 - (PTA\ post - PTA\ pre) / (PTA\ max - PTA\ pre)$$

In this equation, HP is Hearing preservation, PTA_{pre} is the average pure-tone (unaided) hearing threshold of 125, 250 and 500 Hz measured preoperatively, PTA_{post} is the same average pure-tone hearing threshold measured postoperatively, and PTA max is the maximum sound intensity generated by a standard audiometer (usually between 90-120 dB HL) (Skarzynska et al., 2018).

2. Scalar positioning of the electrode array

We will use the cone beam CT scanner to postoperatively assess the scalar location of the electrode array for all four groups. The CB-CT has been proven to be the best imaging modality for assessing the scalar location postoperatively, as it has low radiation artefacts (caused by the metal parts of the cochlear implant) and high spatial resolution needed to image the cochlea and its internal parts. In addition, it has relatively low radiation exposure, is less likely to trigger claustrophobic reactions and requires shorter scanning durations compared to traditional CT scanners (Li, 2013, Nardi et al., 2018, Casselman et al., 2013).

We will assess CI translocation by making multiplanar midmodiolar reconstructions of the cone beam CT images, which is validated by numerous papers (Mosnier et al., 2017, Zou et al., 2015, Saeed et al., 2014). These multiplanar reconstructions will allow us to systematically indicate for every stimulation point of the cochlear implant the exact scalar position (i.e. scala tympani or scala vestibuli). The main researcher and an experienced otologist will analyse the CT scans blindly for each patient.

3. ECochG

'Electrocochleography' (ECochG) is a method for recording the electrical potentials of the cochlea. The ECochG is composed of several components: the compound action potential (CAP), cochlear microphonics (CM) and the summating potential (SP). In essence, the CAP is generated by the auditory nerve activity, the CM and SP are generated by the hair cells of the

organ of Corti. The CM is an AC response following the tone, and the SP is a DC response. Outcome measures include the CM amplitude and the total ECochG amplitude. Potentially, the difference in the amplitude of the total ECochG response after and before insertion might contain information about insertion trauma, i.e. damage to the basilar membrane, stria vascularis or other structures.

We will use the most apical contact point of the electrode array to measure these outcomes. The acoustic pure tones and click stimuli will be delivered via the insert earphone. This will be coupled to the measurement equipment that is provided with the CI by the manufacturer. The amplifier in the implant will be used for amplification of the response.

4. Speech perception scores

One year after cochlear implantation, a conventional speech perception test with/without noise test will be performed with CVC words from the 'Nederlandse Vereniging voor Audiologie' (NVA) word-list. The speech tests can be quantified with a simple correct percentage score. Also, the clinical ripple test, which uses tones instead of words, can be used to complement speech perception scores (Drennan et al., 2014).

5.4 Withdrawal of individual subjects

Subjects can leave the study at any time for any reason if they wish to do so without any consequences. The investigator can decide to withdraw a subject from the study for urgent medical reasons.

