3. STUDY DESIGN

The study design is illustrated in **figure 3**:

This study concerns a single-blind mono-center randomized controlled, with 18 year and older severely or profoundly hearing-impaired patients who are eligible for a cochlear implant. Every candidate for cochlear implantation needs to have severe hearing loss bilaterally, should not have contraindications for surgery and should be able to follow an intensive medical rehabilitation program. The study will be performed at the department of Otorhinolaryngology in the University Medical Center Utrecht, and will run till 01-01-2027.

[figure not shown]
All participants will undergo the usual standard medical care of work-up before cochlear implantation. The work-up includes a pure tone audiogram (PTA), a speech audiogram, a preoperative CT, and interviews with speech therapist, audiologist, ENT surgeon and social worker. In a multidisciplinary meeting, the Cochlear implantation team of the UMC Utrecht will assess all results and decides whether a patient is suited for a cochlear implant.

Eligible cochlear implant candidates will then for this study be randomized to group 1 (RW + LW), 2 (CO + LW), 3 (RW + PM) or group 4 (CO + PM).

Study procedures:

For all patients, during implantation, the standard measurements for eCAP and electrode impedances and the experimental measurements of ECochG will be performed. Postoperatively, a cone beam CT scan will be made to assess the scalar position of the CI. After activation of the CI, which is usually around three to four weeks postoperatively, the ECochG measurements will be repeated. For this study, we add two extra pure tone audiograms at 6 /12 months, resulting in a total of 4 audiograms (at one three, six and 12 months). Pure tone audiometry is without CI, which will allow us to determine the residual acoustic hearing capability of the patients. At 12 months, a conventional speech perception test with consonant-vowel-consonant (CVC) word score with/without noise will be performed. The speech perception test is with CI and determines the maximal electrical hearing capability of the patients. Finally, at 12 months, we will add a spectral ripple test, allowing us to measure hearing performance independent of cognitive and linguistic skills (Drennan et al., 2014).

Study Design

Light grey: Standard medical care

Dark grey: Extra for study

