5.5 Replacement of individual subjects after withdrawal

Subjects who withdraw from the study or who terminate the recording session prematurely will be considered as lost and will be replaced. Reasons for withdrawal or premature termination will be documented. We expect a withdrawal rate of subjects of no more than 10% (since N=48, this is 5). The number of replacements will be limited to two persons per subgroup.

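### Section 5.5 replaces every subject who withdraws, before or after implantation, so patients already randomised and operated on can be substituted in the comparison of hearing preservation

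*Protocol*

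**What the plan says.** Section 5.4 gives two routes out of the study. The first is the subject's own choice: "Subjects can leave the study at any time for any reason if they wish to do so without any consequences". The second is a safety provision: "The investigator can decide to withdraw a subject from the study for urgent medical reasons". Neither is limited to the time before surgery.

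Section 5.5 sets the consequence: "Subjects who withdraw from the study or who terminate the recording session prematurely will be considered as lost and will be replaced". It makes no distinction by timing or reason. It adds that "Reasons for withdrawal or premature termination will be documented", caps replacements at two per subgroup, and gives the expected loss as at most 10% of 48, or 5 subjects.

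Section 5.6 ends follow-up of withdrawn subjects who have no adverse event. Section 6.3 follows adverse events until they resolve or settle.

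Section 5.3 places randomisation after the preoperative work-up, and so before the operation. Section 7.1 compares HP between the four groups by ANOVA.

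**The concern.** The intervention is one operation. Once the array is in place, leaving the study does not undo or shorten the exposure; it only stops measurement. The usual case for replacement, that a subject left without receiving the intervention, therefore applies only before implantation.

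After implantation, a decision to leave may be related to how the operation turned out. A subject with a disappointing result may see little point in further visits. If such a patient is classed as lost and a new one takes the place, the comparison depends in part on a consequence of the allocated technique. The arm with more poor results would then look better than it is.

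The endpoint gives no reason to stop measuring. The pure tone audiogram is taken without the implant, so it can be obtained whether or not the patient uses the device. Replacement and the end of follow-up are also conduct rules fixed in the protocol. An analysis plan could keep withdrawn patients in the analysis set, but it could not supply audiograms that were not made.

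**Working it through.** **1. Do the rules reach an implanted patient?** Yes. Sections 3 and 5.3 give the order: work-up, randomisation, surgery with ECochG, postoperative cone beam CT, then audiograms at about 1, 3, 6 and 12 months. Take a subject who leaves between months 3 and 6. The intraoperative ECochG, the scan and two postoperative audiograms should already exist. Section 5.5 still classes the subject as lost and calls for a replacement. With no adverse event, section 5.6 ends follow-up.

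**2. Does anything else in the protocol secure the outcome?** Only in part. Section 5.6 implies continued follow-up when there is an adverse event, but section 6.3 describes follow-up of the event and does not mention audiometry. Documented reasons show why a patient left; they do not supply the missing HP value.

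**3. Planning figures (section 4.4).** Within-group SD 35, group means around 50, difference of 40 between best and worst group, between-group SD 20, 12 per group. Effect size f = 20/35 = 0.57. One-way ANOVA, 4 groups, noncentrality 48 × 0.57² = 15.6, 3 and 44 degrees of freedom, alpha 0.05 (an assumption; the protocol states none): power 0.902, or 0.903 with f unrounded. The stated 0.9 is reproduced, so these figures can be used below.

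**4. How many replacements are possible?** Expected withdrawals: 10% × 48 = 4.8, i.e. 5. If a subgroup is a treatment group, the cap is 4 × 2 = 8, or 8/56 = 14.3% of all randomised. If it is a treatment group within an age stratum, the cap is 8 × 2 = 16.

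**5. Shift in one arm's mean.** If k patients with HP 0 are replaced by patients at the arm's average, shift = k × (arm mean − 0)/12.

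| Arm mean | k = 1 | k = 2 |
|---|---|---|
| 50 | 50/12 = 4.2 | 100/12 = 8.3 |
| 30 | 30/12 = 2.5 | 60/12 = 5.0 |
| 70 | 70/12 = 5.8 | 140/12 = 11.7 |

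At mean 50 the shifts are 4.2/40 = 10% and 8.3/40 = 21% of the target difference.

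**6. Worst-case simulation.** Outcomes were normal with SD 35, and the worst k of 12 + k patients in an affected arm were removed. The mean rises by about 4.8 points (k = 1) or 8.6 points (k = 2), close to step 5. With four equal true means, the type I error of the nominal 5% test is:

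- no replacement: 0.05
- worst 1 replaced in one arm: 0.07
- worst 2 replaced in one arm: 0.09
- worst 2 replaced in each of two arms: 0.12
- worst 2 replaced in all four arms: 0.11 (here the arms are treated alike; the excess comes from the narrowed within-group spread)
- the same numbers removed at random: 0.05 throughout

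With true means 70, 70, 30 and 30, power falls from 0.90 to 0.85 if the worst patient is replaced in each of the two poorer arms, and to 0.78 if the worst two are.

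**The case against.** A reader might infer from sections 5.4 and 5.5 together that investigators who know the allocation can remove surgical failures from the trial. The documents do not support that.

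- The sentence in 5.4 is an ordinary safety provision. Nowhere does the protocol make a poor insertion, a translocation or lost residual hearing a reason for withdrawal. Scalar position and hearing preservation are endpoints, and a poor result on either is not evidently an urgent medical reason. A serious complication might qualify; how often is not stated.
- Section 5.5 speaks of subjects who withdraw. Its heading and position make it reasonable to include withdrawals by the investigator, but the text does not say so.
- On blinding, section 5.2 says "This study is single-blind, meaning that only participants are blinded for the treatment allocation", but its next sentence adds that research assistants are blinded, and section 5.3 has the scans read blind. The investigator who decides on a withdrawal is in neither group. That alone does not show selective withdrawal.

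A reader might also infer that data already collected are discarded. Section 5.5 does not say so, section 7.1 names no analysis set, and an analysis plan not shown here may settle it.

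The size can be challenged too. An 8.3-point shift needs two complete losses of hearing, both withdrawn, both in one arm, out of about 5 withdrawals for any reason. The standard error of an arm mean is 35/√12 = 10.1, so even that shift is below one standard error. Documented reasons would make a pattern visible.

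Finally, routine records alone recover little after month 3, because section 3 says "For this study, we add two extra pure tone audiograms at 6 /12 months, resulting in a total of 4 audiograms". That is correct, and the later audiograms would have to be offered.

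What remains does not depend on the investigator. A subject's own withdrawal after implantation falls under 5.5 on any reading, and the patient is then replaced and, without an adverse event, no longer followed.

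**Conclusion.** The point holds as one about the replacement rule in 5.5 and the end of follow-up in 5.6. An implanted, randomised patient can be substituted and later audiograms not taken. Bias follows only if withdrawal after implantation is related to the surgical result, whether by the subject's choice or, if 5.5 is read to include it, by an investigator's withdrawal.

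The documents give no frequency, so the bias cannot be estimated. The shifts of 4.2 and 8.3 points and the type I error of up to about 0.12 are illustrations under deliberately adverse assumptions: outcomes at or near the bottom of the scale, replacement up to the cap on the treatment-group reading, and alpha 0.05. Withdrawal unrelated to outcome leaves the comparison unbiased. This is a cheap improvement to a stated conduct rule, not a flaw that invalidates the design.

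**What to change.** - **Section 5.5:** allow replacement only for subjects who leave before implantation. State that every implanted subject stays in the randomised group, with all data collected up to withdrawal. Any extra patients recruited to keep numbers up are added to these subjects and do not take their place.
- **Section 5.6:** unless the subject refuses, continue to extract routine audiograms from the health record, which section 9.1 already uses as a source, and offer the remaining unaided audiograms.
- **Section 5.4:** leave the withdrawal criterion as it is.

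Cost: an amendment to two short sections and one line in the consent form. The downside is that a few implanted subjects will have incomplete 12-month data, which the analysis must handle.

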5.5 Replacement of individual subjects after withdrawal

Subjects who withdraw from the study or who terminate the recording session prematurely will be considered as lost and will be replaced. Reasons for withdrawal or premature termination will be documented. We expect a withdrawal rate of subjects of no more than 10% (since N=48, this is 5). The number of replacements will be limited to two persons per subgroup.

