2. OBJECTIVES

Primary Objective:

To compare hearing preservation percentage after cochlear implantation between two surgical approaches (CO, RW) and two electrode array designs (LW, PM).

Secondary Objective(s):

- To determine the relationship of scalar position of the electrode array and hearing preservation (i.e. residual acoustic hearing).
- To determine the relationship of scalar position of the electrode array and hearing performance after one year with CI.
- To assess residual hearing over time after implantation.
- To find which ECochG measures can be used best for assessment of insertion trauma.
- To determine the relationship between ECochG measures and residual hearing and speech perception postoperatively.
- To determine the relationship between ECochG measures and scalar position of the electrode array.

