5.6 Follow-up of subjects withdrawn from treatment

Subjects who withdraw from the study or who terminate the recording session prematurely, in the absence of any adverse event, will not be followed.

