8.5 Incentives (if applicable)

All participants will receive compensation for travel expenses made: €0.19 per kilometer travelling distance for study related visits to the outpatient clinic for the 6 and 12 months session after CI surgery. The subjects will be compensated for travel expenses made, irrespective of whether the test sessions are planned on the same day as routine follow-up visits or if participation is prematurely stopped.

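### Ending an undefined recording session early is handled like withdrawal, so a randomised patient who could still give audiograms leaves study follow-up

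*Protocol*

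**What the plan says.** Section 5.5 of the protocol sets the rule: "Subjects who withdraw from the study or who terminate the recording session prematurely will be considered as lost and will be replaced". Section 5.6 repeats the pairing of withdrawal with an early-ended session and says that these subjects, "in the absence of any adverse event, will not be followed".

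Section 5.4 describes how a subject leaves the study. The subject may leave at any time for any reason, or "The investigator can decide to withdraw a subject from the study for urgent medical reasons". It does not mention an unfinished session.

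The primary outcome is hearing preservation, calculated from pure tone audiometry without the implant (sections 5.1.1 and 5.3). Postoperative audiograms are due at about 1, 3, 6 and 12 months. Section 3 says the 6 and 12 month audiograms are added for the study. One secondary objective in section 2 is "To assess residual hearing over time after implantation".

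Section 5.5 expects no more than 10% withdrawals, given as 5 of 48. It also states: "The number of replacements will be limited to two persons per subgroup".

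**The concern.** Leaving the study and not finishing one measurement session are different events. A patient who stops a session because of fatigue or discomfort has not necessarily refused the next audiogram. Sections 5.5 and 5.6 nevertheless put this patient in the same class as one who withdraws: lost, replaced and, absent an adverse event, not followed.

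Randomisation precedes surgery and every postoperative session, so the loss falls after randomisation. The trial plans only 12 patients per arm. An audiogram that was never made cannot be restored by any later analysis plan, so the protocol itself has to settle this point. If the primary comparison were then run on completers plus replacements, the arms would no longer be compared strictly as randomised.

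**Working it through.** **1. What recording session can mean.** The term appears only in sections 5.5 and 5.6. Two readings fit the protocol.

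- *The ECochG recording.* Section 5.3 uses the verb record for ECochG potentials, and section 5.1.2 lists ECochG as secondary. Nothing in the protocol makes audiometry depend on a completed ECochG recording. On this reading, an unfinished secondary measurement ends follow-up for the primary outcome.
- *A whole test visit.* Section 8.5 uses session in this sense, for "study related visits to the outpatient clinic for the 6 and 12 months session after CI surgery" and for the case where "the test sessions are planned on the same day as routine follow-up visits". Section 5.3 pairs audiometry with ECochG at activation and at 3, 6 and 12 months, so a shortened visit may lack its own audiogram. The other scheduled audiograms are unaffected, yet the rule ends study follow-up for those too.

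**2. What is forgone.** Of the four postoperative audiograms, two (6 and 12 months) are study additions, so the earlier two belong to usual care. Section 9.1 has audiogram results extracted from the health record. What the rule gives up is therefore mainly the 6 and 12 month audiograms.

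**3. The plan's own power figure.** Inputs from section 4.4: four groups of 12, effect size f = 0.57, one-way fixed-effects ANOVA. Alpha is not stated there; 0.05 is assumed. With noncentrality λ = N × f²:

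- N = 48: λ = 48 × 0.57² = 15.6, df 3 and 44, power 0.902. The stated 0.9 reproduces.
- N = 43 (five patients without a usable value and not replaced): λ = 43 × 0.57² = 14.0, df 3 and 39, power 0.860. Arms are treated as near balanced.

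**4. How large a bias could be.** The protocol gives no number for early-ended sessions. Its 10% (0.10 × 48 = 4.8, rounded to 5) is a withdrawal rate. The figures below also assume that the analysis uses completers plus replacements, which the protocol does not say.

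- *Loss at random:* no bias.
- *The 5 or 8 worst of all 48 leave regardless of arm and are replaced at random:* simulated type I error of the four-arm ANOVA is 0.051 and 0.049, against 0.051 with no loss.
- *Extreme case, only the worst one or two of 12 in a single arm leave:* the expected lowest two standard normal values of 12 are −1.63 and −1.12. With the SD of 35 from section 4.4, the arm mean rises by 1.63 × 35 / 12 = 4.8 points, or by (1.63 + 1.12) × 35 / 12 = 8.0 points. Both are below one standard error of an arm mean, 35 / √12 = 10.1, and well below the design difference of 40. Simulated type I error is then about 0.065 and just over 0.08.

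The last case is a bound and not a forecast.

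**The case against.** The strongest reply is that the clause is loosely worded withdrawal. Both sentences stand under headings about withdrawal, the subject is the one who terminates, and section 5.4 allows leaving for any reason. That reading is possible. But the text joins the two cases with an or, and section 5.4 already covers real withdrawal, so on this reading the clause adds nothing and can be deleted at no cost.

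Several further objections stand and limit the point.

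- A reader might infer that patients are dropped because the allocated approach or array made an intraoperative recording fail. The rule speaks of subjects who terminate, not of a technical or surgical failure, and section 5.2 blinds participants to allocation. Arm-related loss is thus less likely, although outcome-related loss is not excluded.
- A reader might infer that collected audiograms are discarded or that the primary analysis excludes these patients. The protocol says neither. The analysis set may be defined in a statistical analysis plan that is not shown.
- Earlier audiograms are routine, and section 5.5 has reasons for leaving documented, which allows partial checking.

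It might also be said that replacement protects the trial. It restores the count, but it does not supply the outcomes of the randomised patients who left.

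**Conclusion.** The point holds as avoidable loss of follow-up after randomisation, written into sections 5.5 and 5.6. It does not depend on which meaning of recording session is right, because under both a patient able to give later audiograms leaves the study. What is lost is mainly the 6 and 12 month audiograms.

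The documents do not support a claim that the primary comparison is biased. Size and direction are unknown, and the calculated shifts are small against the design difference even in an extreme case. The number of patients affected is also unknown.

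The replacement cap is a matter of wording only. Section 5.5 does not say what a subgroup is, while section 5.2 uses the word for age: "They will stratify the groups for age, with two subgroups, 18-50 years and > 50 years". Two per arm (2 × 4 = 8 replacements) fits the expected 5 losses most comfortably; two per age stratum (2 × 2 = 4) would fall below them.

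Severity: minor to moderate.

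**What to change.** 1. Delete the early-ended-session clause from sections 5.5 and 5.6, so that both apply only to subjects who withdraw.
2. State that an incomplete session makes only the unmeasured values missing, and that the subject stays in audiometric follow-up in the allocated arm unless he or she withdraws under section 5.4.
3. State that audiograms already obtained and, with consent, later routine-care audiograms remain available for the primary comparison even if a withdrawn subject is replaced.
4. Say what subgroup means in the replacement cap.

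The cost is amendment wording and a line in the consent text, with no visits beyond those planned. The downside is that patients who end a session early are no longer replaced. Any who lack a value at the analysed time point reduce the analysed number, as in the N = 43 calculation above. Replacement of patients who truly withdraw continues under the existing cap.
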